### 12.1. Adverse Events

AEs for all patients in the safety population will be included in the AE summaries.

Adverse events will be summarized by system organ class (SOC) and preferred term (PT) for each treatment and Orismilast total, based on the MedDRA dictionary version 24.0. Severity of AEs will be graded according to National Cancer Institute (NCI) Common Terminology Criteria for Adverse Events (CTCAE) version 5.

Any AEs that occur before dosing on study Baseline will be categorized as pretreatment events. TEAEs will be defined as those AEs that occur or worsen in severity after initial dosing and up to 7 days after the last dose of study drug.

Duration will be calculated for AEs that resolve as the difference between the resolution date and onset date plus 1 and expressed in days.

The summary tables will include the number of patients and the number of events. Percentages will be based on the number of patients in the safety population. For summaries by SOC and PT, a patient will be counted once at the SOC level and once at each PT within the SOC level.

For summaries by SOC, PT, and maximum severity, a patient will be counted once at the highest severity level for which the event occurred at the SOC level and the highest severity level for each unique PT within that SOC level. Therefore, patients may only contribute once to each PT and once to each SOC level.

The summaries presenting frequency of AEs by SOC and PT will be ordered by Orismilast total descending frequency of SOC and then, within a SOC, by Orismilast total descending frequency of PT.

The following tables will be provided:

- An overall summary of the number of events and number and percentage of patients reporting TEAEs, related TEAEs (TEAEs recorded as “Relationship to study drug” = “Possibly” or “Probably” or “Definitely”), serious TEAEs (TESAEs), TEAEs resulting in death, TEAEs of special interest, TEAEs leading to study drug discontinuation, TESAEs leading to study drug discontinuation, TEAEs by relationship and TEAEs by toxicity grade;
- TEAEs overall by system organ class and preferred term;
- An overall summary of the number of events and number and percentage of patients reporting TEAEs, related TEAEs (TEAEs recorded as “Relationship to study drug” = “Possibly” or “Probably” or “Definitely”), serious TEAEs (TESAEs), TEAEs resulting in death, TEAEs of special interest, TEAEs leading to study drug discontinuation, TESAEs leading to study drug discontinuation, TEAEs by relationship and TEAEs by toxicity grade starting within the dose titration period (initial 3 weeks)

This document is confidential.

- TEAEs overall by system organ class and preferred term starting within the dose titration period (initial 3 weeks)
- TEAEs by maximum toxicity grade, overall and by system organ class and preferred term;
- TEAEs by toxicity grade, overall and by system organ class and preferred term;
- TEAEs by maximum relationship to study medication, overall and by system organ class and preferred term;
- TEAEs by relationship to study medication, overall and by system organ class and preferred term;
- TESAEs, overall and by system organ class and preferred term;
- TESAEs by maximum toxicity grade, overall and by system organ class and preferred term;
- TESAEs by toxicity grade, overall and by system organ class and preferred term;
- TESAEs by maximum relationship to study medication, overall and by system organ class and preferred term;
- TESAEs by relationship to study medication, overall and by system organ class and preferred term;
- TEAEs leading to study drug discontinuation, overall and by system organ class and preferred term;
- TEAEs leading to death, overall and by system organ class and preferred term;
- TEAEs of special interest, overall and by system organ class and preferred term;
- AEs starting in the 4-week Follow-up period overall by system organ class and preferred term;
- SAEs starting in the 4-week Follow-up period overall and by system organ class and preferred term;

Only TEAEs will be included in the summary tables, however separate listings for treatment-emergent AEs, non-treatment-emergent AEs, AEs starting within the dose titration period (initial 3 weeks) and AEs starting in the 4-week Follow-up period will be generated. Additional listings will be provided for deaths, AESIs, serious AEs and Adverse Events Leading to Study Drug Discontinuation.

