5.3. Clinical Risks/Benefits

Despite the positive and encouraging efficacy results of the Phase 2a study of the immediate-release tablets of orismilast, this formulation presented an undesirable safety profile with 50% of patients prematurely discontinuing because of GI effects. To improve the GI tolerance, several formulations were tested in an extensive Phase 1 clinical program, leading to the selection of a modified-release formulation with notably better GI tolerance in healthy volunteers. The modified-release formula is expected to mitigate potential GI effects previously observed in psoriasis patients with the immediate-release tablets while maintaining the efficacy previously observed. The titration dosing schedule at the initiation of study treatment will help to reduce the incidence and severity of GI side effects that tend to occur primarily when starting therapy. The improved safety profile of the modified-release formulation is expected to make the therapeutic window of orismilast wider this allowing to achieve dosing levels with adequate efficacy and good tolerability.

Occurrence and severity of GI disorders will be promptly identified by monitoring the subjects for any signs of abdominal discomfort, abdominal distension, abdominal pain, nausea, vomiting, loss of appetite, and diarrhea. Depending on their severity, these AEs may qualify as an adverse event of special interest (AESI). Based on the occurrence of GI or other AEs considered having a causal relationship with study treatment, the Investigator might consider decreasing the daily dosing regimen or stopping the treatment for a few days, until recovery. Besides the above, all subjects will be monitored for any cardiovascular manifestations using vital signs and 12-lead ECG at each visit. Drug class potential effects such as weight loss and major depression will be monitored during the study. Subjects with major depression, presenting major psychiatric disorders or at risk for suicide will be excluded from enrollment, and suicidal ideation and depressive symptoms will be assessed in the course of the study by Columbia-Suicide Severity Rating Scale (C-SSRS) and Hospital Anxiety and Depression Scale (HADS), respectively. Patients will be informed of the potential increased risk of depression or suicidal thoughts of this class of drugs; and recommended to promptly contact their study doctor in case of such event.

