#### **3.2. Secondary Objective**

Evaluate the dose response of orismilast and identify the dose with the best benefit/risk ratio to be evaluated in a Phase 3 program.

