### 7.2. Key Definitions

#### Treatment period

The Treatment Period for this study is 16 weeks, from Day 1 to Week 16 (112 ± 3 days).

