## **8.7. Extent of Exposure**

Study drug administration data including dates for administration, dispensing and dose interruption details will be listed for all patients in the ITT population.

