## 12. Safety

All safety analyses will be conducted using the safety population.

Safety will be assessed based on adverse event (AE) reports, physical examination, vital signs, ECGs, clinical laboratory data, HADS and C-SSRS using descriptive statistics.

No inferential statistical analyses are planned on the safety parameters of this study.

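### TEAEs are summarised only as counts and crude percentages although time at risk ends 7 days after each patient's own last dose; if early stopping differs by dose, later-onset events are understated in the arm with the shortest time at risk

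*SAP*

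**What the plan says.** SAP 12.1 defines TEAEs as "those AEs that occur or worsen in severity after initial dosing and up to 7 days after the last dose" of study drug. Its tables give the number of events and the number of patients by arm, and "Percentages will be based on the number of patients in the safety population". SAP 12 adds that "No inferential statistical analyses are planned on the safety parameters of this study".

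Exposure is handled separately. Under SAP 8.7, dosing dates and "dose interruption details will be listed for all patients in the ITT population". Days of dosing are summarised by arm in the compliance table (SAP 8.8). SAP 8.1 plans a Kaplan-Meier plot of time to treatment discontinuation.

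Two sets of AE tables use other windows: TEAEs starting in the first 3 weeks, and AEs and SAEs starting in the 4-week Follow-up period (SAP 12.1). Neither SAP 12.1 nor the table and figure indexes (SAP 18 and 19) contains a rate per patient-time or a time-to-first-event display for AEs.

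The safety results feed the secondary objective (SAP 3.2), which is to evaluate dose response and "identify the dose with the best benefit/risk ratio to be evaluated in a Phase 3 program".

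**The concern.** A crude percentage compares arms fairly when patients in each arm are watched for about the same time. Here the watching time depends on when each patient stops. An arm that loses more patients early has fewer weeks in which a later event can count as a TEAE, but keeps its full denominator.

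Unequal stopping is plausible. Protocol 5.2.2.3 reports that AEs became more frequent and more severe as the dose rose, and Protocol 9.3 ends dosing after a severe TEAE. The events exposed to this problem take weeks to appear, and some are risks that the protocol picks out: "Drug class potential effects such as weight loss and major depression will be monitored during the study" (Protocol 5.3). When the columns are read side by side to choose a Phase 3 dose, a less well tolerated dose could look better on such events than it is.

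**Working it through.** **Plan's own figure.** The plan states no AE incidence, time at risk or expected discontinuation rate, so there is none to reproduce on this point. Its one calculated figure, 80% power with 50 per arm (SAP 4.3), reproduces (difference 18.7, SD 33, two-sided 5%: 80.1% by the noncentral t distribution) but does not bear on the AE tables.

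**Inputs from the documents**
- Treatment period 112 days (SAP 7.2); TEAE window to last dose + 7 days (SAP 12.1). Full window 112 + 7 = 119 days = 17 weeks. Stopping at Week 2 gives 14 + 7 = 21 days = 3 weeks.
- AE-related withdrawal in the Phase 2a trial of the immediate-release tablet: 50% on drug, 16.7% on placebo (Protocol 5.2.2.3). Withdrawal for any reason: about half in both arms (Protocol 5.2.2.2).

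**Assumptions.** A 20% risk over the full 17 weeks at constant hazard; the stopping fractions f; and stop times either spread evenly over 16 weeks or all at one week s.

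**Formulas.** Weekly hazard h = −ln(1 − 0.20)/17 = 0.01313.
- All stop at week s: crude = (1 − f)(0.20) + f[1 − e^(−(s+1)h)]. The bracket is 0.0386 for s = 2 and 0.0635 for s = 4.
- Stops spread evenly: the bracket becomes 1 − [e^(−h) − e^(−17h)]/(16h) = 1 − (0.98696 − 0.80000)/0.21002 = 0.1098.

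**Results, with the same true hazard in both arms**

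| Arm A | Arm B | Crude A | Crude B | Ratio |
|---|---|---|---|---|
| 25%, even | 16.7%, even | 17.7% | 18.5% | 0.96 |
| 50%, even | 16.7%, even | 15.5% | 18.5% | 0.84 |
| 50%, Week 4 | 50%, even | 13.2% | 15.5% | 0.85 |
| 50%, Week 2 | none | 11.9% | 20.0% | 0.60 |

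Second row in full: A = 0.5 × 0.20 + 0.5 × 0.1098 = 0.155; B = 0.833 × 0.20 + 0.167 × 0.1098 = 0.185. The third row shows that equal stopping fractions still leave a gap when the timing differs.

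**First-event rate.** At constant hazard, first events divided by time to first event or end of window estimate h in every arm: 0.01313 × 100 × 365.25/7 = 68.5 per 100 patient-years. The rate ratio is therefore 1.00 in all four rows.

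**Where a rate falls short.** Take a 10% risk over 119 days that starts only after day 28, a true hazard ratio of 1.5, and stopping at day 28 by 50% on active and 16.7% on placebo. The crude percentages are 7.9% and 8.5% (ratio 0.93, direction reversed). The whole-period rate ratio is 1.28. Time-to-event risk at day 119 is 14.6% versus 10.0%. The rate corrects late onset only in part.

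**Do the Follow-up tables restore the lost weeks?** No. The Follow-up visit falls 4 weeks after completion or discontinuation (Protocol 7.1), and AE collection ends there (Protocol 12.9.1). Collection after the first dose lasts about 6 weeks for a Week 2 stopper and 20 for a completer. With 50% stopping at day 14, mean time is 0.5 × 140 + 0.5 × 42 = 91 days, or 65% of 140; with stopping at day 56 it is 112 days, or 80%.

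**The case against.** **Size.** Safety is descriptive, treatment is fixed at 16 weeks, and a crude on-treatment percentage is a legitimate quantity. With 50 per arm, 15.5% versus 18.5% is 7.75 versus 9.25 patients, a gap of 1.5. The standard error of a single 20% proportion is √(0.2 × 0.8/50) = 5.7 points. This stands: at moderate differences in stopping the distortion is smaller than chance variation. It is systematic, however, and the tables do not show it.

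**A stronger reading of the size.** A reader might infer that early stopping alone would make the top dose look 20–40% safer (25% or 50% stopping at Week 2 gives ratios of 0.80 and 0.60). The documents do not support that. It sets the arm against one with no stopping at all and puts every stop at Week 2. In the Phase 2a trial about half of both arms withdrew, on placebo mainly for lack of efficacy. What matters is the difference between arms, and its direction against placebo is uncertain.

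**A stronger reading of the cause.** A reader might also infer that the plan expects discontinuation to rise with dose. It says no such thing. The Phase 2a withdrawals and the poor tolerability of higher tablet doses concern the immediate-release form. Protocol 5.3 expects the modified-release tablet to be better tolerated.

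**Other displays.** The first-3-weeks tables give a near-common window for early GI events. The Kaplan-Meier plot shows when patients stop. HADS and C-SSRS are tabulated by visit (SAP 12.6 and 12.7), and weight change at Week 16 is tabulated (SAP 9.2.3). So depression and weight do not rest on TEAE percentages alone, although those displays have dropout limits of their own. Event counts and days of dosing would let a reader approximate an event rate. But events may include repeats, and days of dosing is not time at risk.

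**Conclusion.** The point holds conditionally. The TEAE window and the denominator together make crude percentages depend on when patients stop, and no planned output relates AEs to time at risk. If stopping differs between doses in amount or timing, later-onset events are understated in the arm with the shortest time at risk. Early GI events are little affected.

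The documents give no expected stopping rate, so the size can only be shown as a range: a ratio of about 0.96 for 25% versus 16.7% stopping, 0.84 for 50% versus 16.7%, and 0.60 in the extreme case. These figures assume constant hazard, a 20% event, the same true hazard in both arms and, except in the extreme case, stops spread evenly. That stopping rises with dose is an inference from the AE pattern of other formulations. This is a cheap improvement to the safety reporting, not an error that invalidates it.

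**What to change.** - **SAP 8.7:** summarise time at risk by arm, from first dose to last dose + 7 days.
- **SAP 12.1 and the table index:** keep the crude percentages. Beside them give first-event rates per 100 patient-years at risk for any TEAE, serious TEAEs, each AESI category and the most frequent preferred terms.
- **SAP 12.1 and the figure index:** add descriptive cumulative incidence curves for the weight-loss and depression AESIs, censored at the end of the TEAE window.
- **State the assumptions.** A rate assumes constant hazard and only partly corrects late onset, which is why the curves are needed. Censoring at the end of the window assumes that stopping is unrelated to later event risk. That is doubtful where a severe TEAE itself ends dosing (Protocol 9.3), and the SAP should say so.
- **Use one window.** SAP 5.5 describes TEAEs over treatment and the 4-week Follow-up Period, while SAP 12.1 closes at 7 days. Reconcile the two, so that events and time at risk cover the same period.

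**Cost:** two or three extra outputs from data already collected, with no change to visits or treatment. With 50 per arm some rates and curves will rest on few events and should be read as descriptive.

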7.2. Discussion of Study Design

A double-blind, randomized, placebo-controlled study is considered a gold-standard for conducting any interventional and dose-finding study. A sample size of 50 patients per treatment arm is also adequate to get robust outcome data for a comparison among doses and with placebo.

Psoriasis is a chronic condition requiring long-term therapy. Primary efficacy assessments of psoriasis clinical trials are usually performed at 12 or 16 weeks after initiation of study treatment. Because of the initial titration period of up to 2 weeks duration, a treatment duration of 16 weeks, with the primary endpoint being evaluated at this time point is, therefore, considered the optimal strategy for this study. Primary evaluations of apremilast, the only PDE4 inhibitor currently approved for psoriasis treatment, were also conducted at Week 16. A 16-week Treatment Period was also deemed acceptable for the placebo arm because psoriasis is not a life-threatening disease warranting immediate treatment.

Besides the usual psoriasis assessments including the PASI, the IGA, and the BSA, the effects of study treatment on nail and scalp psoriasis that represent location of disease more refractory to treatment will be explored. In patients with PsA, any potential effect on will be also assessed. A number of patient-reported outcome (PROs) will be administered to explore the patient's perception of his or her condition and the related QoL, as recommended by regulatory agencies. This comprehensive evaluation of the psoriatic condition of patients will contribute to the selection of the most suitable dose(s) for the Phase 3 clinical program.

^{*}To maintain the study blind.

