9.3.1. Titration

Titration of oral apremilast was shown to improve the GI tolerance and overall acceptability of the drug (Zerilli 2015). Similarly, a slow increase in orismilast dose was associated with less GI side effects when compared with a rapid increase. Consistent with this approach, this study will titrate the study treatment dose over a period of maximum 2 weeks (see Table 2).

If tolerability issues arise during the treatment up-titration and/or during maintenance period, the following treatment pauses are allowed only if instructed by the Investigator:

- First day: The Investigator is informed of the tolerability issue; thus, the evening dose can be skipped.
- Second day: Morning dose can be skipped. The patient must take the evening dose.
- Third day: Similar to Day 2, morning dose can be skipped. The patient must take the evening dose.
- Fourth day: BID daily dosing regimen is reintroduced.

The aforementioned treatment pauses do not impact calculation of dosing days and duration of titration is not prolonged. Treatment pauses will be captured in the eCRFs. This titration will not break the blind as all patients will receive 2 of indistinguishable orismilast or placebo tablets BID.

Table 2. Dose Titration Schedule

Arm	Day 1	Da	y 2	Da	у 3	Da	y 4	Da	y 5	Da	y 6	Da	y 7	Da	ıy 8	Da	y 9	Day	y 10	Day	/ 11	Day	y 12	Day	/ 13	Day	14	From I	Day 15
20 mg BID	10	10	10	10	10	10	10	10	20	10	20	10	20	20	20	20	20	20	20	20	20	20	20	20	20	20	20	20	20
30 mg BID	10	10	10	10	20	20	20	20	20	20	30	20	30	20	30	30	30	30	30	30	30	30	30	30	30	30	30	30	30
40 mg BID	10	10	10	10	20	20	20	20	20	20	30	20	30	20	30	30	30	30	30	30	30	30	40	30	40	30	40	40	40
Placebo	Р	Р	Р	Р	Р	Р	Р	Р	Р	Р	Р	Р	Р	Р	Р	Р	Р	Р	Р	Р	P	Р	Р	Р	Р	Р	Р	Р	P

Abbreviation: BID, twice daily

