## 4. Study Details/Design

### 4.1. Brief Description

This multicenter, randomized, double-blind, placebo-controlled, parallel-group, Phase 2b dose-ranging study is designed to assess the efficacy and safety of modified-release orismilast compared with placebo in adult patients with moderate-to-severe plaque-type psoriasis. Efficacy and safety endpoints will be evaluated to select an appropriate orismilast dose for subsequent Phase 3 studies. The study will be conducted in approximately 40 centers in Europe (Germany, Poland, UK) and US.

After a Screening visit up to 28 days before Baseline, approximately 200 patients will be assigned randomly in a 1:1:1:1 ratio to receive 1 of the 3 orismilast doses (20 mg, 30 mg, or 40 mg) or placebo twice daily (BID) for 16 weeks, with a 4-week Follow-up visit. Administration will begin at Baseline with a dose titration period of up to 14 days (for the orismilast arm only). The maximum duration of study participation is approximately 24 weeks.

Patients will be seen at the site on Screening, Baseline (Day 1), and Weeks 1, 2, 4, 8, 12, 16 (End-of-Treatment [EOT] visit), and 20 (Follow-up visit, 4 weeks after treatment completion or discontinuation). Visits at Weeks 1 and 2 could be conducted via a telemedicine procedure at Investigator's discretion.

At Baseline and each visit from Week 4 onwards, Psoriasis Activity and Severity Index (PASI), body surface area (BSA), Investigator Global Assessment (IGA), and Psoriasis Symptoms Scale (PSS) will be assessed. Quality of life will be assessed by administration of Dermatology Life Quality Index (DLQI) at Baseline and at Weeks 16 and 20 visits. Additional efficacy parameters include: a Scalp-specific Investigator Global Assessment (ss-IGA), a nail psoriasis Physician Global Assessment (PGA-F), and

These parameters will be assessed at Baseline and Weeks 16 and 20. Safety evaluations include adverse events (AEs), laboratory and vital sign assessments, physical examinations as well as mood change evaluation by patient (Hospital Anxiety and Depression Scale [HADS]) and suicidal ideation evaluation by Investigator (Columbia-Suicide Severity Rating Scale[C-SSRS]). A panel of cardiovascular risk factors will be assessed at Baseline and Week 16.

Before administration of the study drug at Baseline and on Weeks 4, 8, and 16, blood will be collected for orismilast concentration determination. In addition, [REDACTED]

[figure not shown]
[REDACTED] See [REDACTED]

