## **8.8. Treatment Compliance**

When patients receive the study drug at the site, they will receive it directly from the investigator or designee who will also give instruction for dose administration. The date of study drug dispensed to the patients will be recorded. At all site visits, patients will return all study drug, including packaging, dispensed at the previous visit.

The dose of study drug and study patient identification will be confirmed at the time of administration by a member of the study site staff other than the person administering the study drug.

When patients self-administer the study drug at home, compliance with the protocol will be assessed at each visit. Compliance will be assessed by direct questioning and counting returned tablets during the site visits. Deviation from the prescribed dosage regimen should be recorded..

A record of the quantity of study drug dispensed to and administered by each patient must be maintained and reconciled with study drug and compliance records. Study drug administration dates, including dates for administration delays and/or dose reductions will also be recorded.

Number of patients with missed doses, number of missed doses, days of dosing, reasons doses were missed and compliance rate will be summarized overall by treatment for the ITT population and separately for the titration period..

This document is confidential.

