	14.3.1.8	Overall Summary of Treatment Emergent Adverse Events (TEAEs) Starting Within the Dose Titration Period (initial 3 weeks)	Safety Population
	14.3.1.9	Treatment Emergent Adverse Events (TEAEs) by System Organ Class and Preferred Term Starting Within the Dose Titration Period (initial 3 weeks)	Safety Population
	14.3.1.10	Summary of Treatment Emergent Adverse Events (TEAEs) by System Organ Class, Preferred Term and Maximum Toxicity Grade	Safety Population
	14.3.1.11	Treatment Emergent Adverse Events (TEAEs) by System Organ Class, Preferred Term and Toxicity Grade	Safety Population
	14.3.1.12	Treatment Emergent Serious Adverse Events (TESAEs) by System Organ Class, Preferred Term and Maximum Relationship	Safety Population
	14.3.1.13	Treatment Emergent Serious Adverse Events (TESAEs) by System Organ Class, Preferred Term and Relationship	Safety Population

This document is confidential.

Header	Table Number	Name	Analysis Population
	14.3.1.14	Treatment-Emergent Non-Serious Adverse Events by System Organ Class and Preferred Term	Safety Population
	14.3.1.15	Treatment-Emergent Adverse Events Leading to Study Drug Discontinuation by System Organ Class and Preferred Term	Safety Population
	14.3.1.16	Treatment-Emergent Adverse Events Leading to Death by System Organ Class and Preferred Term	Safety Population
	14.3.1.17	Treatment-Emergent Adverse Events of Special Interest by System Organ Class and Preferred Term	Safety Population
	14.3.1.18	Adverse Events Starting in the 4-week Follow-up Period by System Organ Class and Preferred Term	Safety Population
	14.3.1.19	Serious Adverse Events Starting in the 4-week Follow-up Period by System Organ Class and Preferred Term	Safety Population
14.3.2		Listings of Deaths, Other Serious and Certain Other Significant Adverse Events	
	14.3.2.1	Listing of Deaths	Safety Population
	14.3.2.2	Listing of Adverse Events of Special Interest	Safety Population
	14.3.2.3	Listing of Serious Adverse Events	Safety Population
	14.3.2.4	Listing of Adverse Events Leading to Study Drug Discontinuation	Safety Population
14.3.3	Not to be used for any Tables	Narratives of Deaths, Other Serious and Certain Other Significant Adverse Events (NOTE: this section is for Medical Writing narratives only, normally not completed by [REDACTED] Biostatistics. No tables should go here. Nevertheless, the section is kept and a note should indicate the responsible party).	
14.3.4		Laboratory, Vital Signs, and Physical Examination Changes	

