	16.2.6.3.5	Exploratory Endpoint: Cardiovascular Risk Factors - Baseline and Week 16	Randomized Population
	16.2.6.3.6	Exploratory Endpoint: PK Levels of Orismilast and Metabolites	Randomized Population
	16.2.6.3.7	[REDACTED]	Randomized Population
16.2.7		Adverse Event Listings	
	16.2.7.1	Treatment-Emergent Adverse Events	Randomized Population
	16.2.7.2	Non-Treatment-Emergent Adverse Events	Randomized Population
	16.2.7.3	Adverse Events Starting Within the Dose Titration Period (initial 3 weeks)	Randomized Population
	16.2.7.4	Adverse Events Starting in the 4-week Follow-up Period	Randomized Population
16.2.8		Listing of individual laboratory measurements by patient	
	16.2.8.1	Clinical Laboratory Data	
	16.2.8.1.1	Clinical Chemistry	Randomized Population
	16.2.8.1.2	Hematology	Randomized Population
	16.2.8.1.3	Urinalysis	Randomized Population
	16.2.8.1.4	Serology	Randomized Population
	16.2.8.1.5	Pregnancy Tests	Randomized Population
	16.2.8.2	Other Safety Data	
	16.2.8.2.1	Vital Signs	Randomized Population
	16.2.8.2.2	Electrocardiogram (ECG)	Randomized Population
	16.2.8.2.3	ECG Overall Evaluation	Randomized Population
	16.2.8.2.4	Physical Examination	Randomized Population
	16.2.8.2.5	Hospital Anxiety and Depression Scale (HADS)	Randomized Population
	16.2.8.2.6	Patients with Suicidal Ideation, Suicidal Behavior, or Self-Injurious Behavior without Suicidal Intent Based on the C-SSRS	Randomized Population

This document is confidential.

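### The SAP's titration-period adverse event outputs cover three weeks, but titration lasts at most 14 days

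*SAP*

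**What the plan says.** SAP 12.1 asks for an overall TEAE summary and a summary by system organ class and preferred term, each limited to events "starting within the dose titration period (initial 3 weeks"), and for a listing over the same window. The indexes carry the wording forward. Table 14.3.1.8 is titled "Overall Summary of Treatment Emergent Adverse Events (TEAEs) Starting Within the Dose Titration Period (initial 3 weeks"), Table 14.3.1.9 uses the same phrase, and Listing 16.2.7.3 is titled "Adverse Events Starting Within the Dose Titration Period (initial 3 weeks").

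The length of titration is given elsewhere as follows:

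- SAP 4.1: "Administration will begin at Baseline with a dose titration period of up to 14 days (for the orismilast arm only").
- Protocol 7.2: "Because of the initial titration period of up to 2 weeks duration".
- Protocol 9.3.1: "this study will titrate the study treatment dose over a period of maximum 2 weeks", and on pauses, "The aforementioned treatment pauses do not impact calculation of dosing days and duration of titration is not prolonged".
- Protocol Table 2: the last column starts at Day 15, where each orismilast arm is at its assigned level.

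SAP 8.8 also has compliance "summarized overall by treatment for the ITT population and separately for the titration period" (Table 14.1.5.2), with no number of days attached there.

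**The concern.** One term has two lengths in the current texts. The protocol's rule that the SAP prevails over it cannot settle this, because SAP 4.1 and SAP 12.1 disagree with each other. SAP section 14, as far as it can be read, lists only the added randomized population as a change from the protocol. No readable passage gives a reason for a three-week window.

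Titration is the protocol's stated means of reducing gastrointestinal side effects at the start of therapy (Protocol 5.3). Choosing the dose with the best benefit/risk ratio is the secondary objective. A table headed as titration-period events will be read as evidence on how well the escalation was tolerated. As written, it also counts events that start after escalation has ended, and the summary tables give no means of separating the two.

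**Working it through.** **Inputs.** The AE window is the initial 3 weeks (SAP 12.1). The titration ceiling is 14 days (SAP 4.1; Protocol 7.2 and 9.3.1). The daily doses come from Protocol Table 2, which has 29 entries per arm: one on Day 1, two a day for Days 2-14, and two for Day 15 onward.

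**Step 1: can 21 days be reproduced?** For each arm, find the first day from which both daily doses stay at the assigned level. Titration days are that day minus 1.

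| Arm | Last step before full dose (two daily doses, mg) | Both doses at assigned level from | Titration days |
|---|---|---|---|
| 20 mg | Days 5-7: 10 and 20 | Day 8 | 8 - 1 = 7 |
| 30 mg | Days 6-8: 20 and 30 | Day 9 | 9 - 1 = 8 |
| 40 mg | Days 12-14: 30 and 40 | Day 15 | 15 - 1 = 14 |

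The longest schedule is 14 days, which reproduces the figure in SAP 4.1 and the protocol. Pauses cannot supply a third week, because Protocol 9.3.1 says they do not lengthen titration. No arm and no variant gives 21 days.

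**Step 2: how far does the window overrun the ceiling?** Assume the initial 3 weeks are study Days 1-21, with study day as defined in SAP 7.2.

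- Days beyond the ceiling: 21 - 14 = 7, and 7/21 = 33.3%.
- If the window is read as the first-dose date plus 21 days (study Days 1-22): 22 - 14 = 8, and 8/22 = 36.4%.

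**Step 3: days with both doses at the assigned level inside each candidate window**, carrying the Day 15 doses forward.

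| Arm | Days 1-21 | Days 1-14 |
|---|---|---|
| 20 mg | 21 - 7 = 14 (66.7%) | 14 - 7 = 7 (50.0%) |
| 30 mg | 21 - 8 = 13 (61.9%) | 14 - 8 = 6 (42.9%) |
| 40 mg | 21 - 14 = 7 (33.3%) | 14 - 14 = 0 (0%) |

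These are shares of scheduled time, not of events. The documents do not allow the share of adverse events affected to be derived.

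**The case against.** The best defence is that this is a naming matter. For the adverse event outputs the SAP gives a single window, used consistently in section 12.1 and both indexes. SAP 4.1 is a short design description and sets no reporting window. The titles print the three weeks, so readers can see what was counted. The sponsor may have wanted an early-tolerability window on purpose. Any common window also mixes phases: even Days 1-14 includes 7 full-dose days for 20 mg and 6 for 30 mg.

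Much of this stands, and it limits the weight of the point:

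- The 33% is measured against the common 14-day ceiling, which only the 40 mg arm reaches. The other arms finish escalating earlier.
- Placebo has no titration. Its column simply uses the same calendar window, so the label alone does not bias comparisons between arms.
- The compliance table is a request for clarity, not an error. SAP 4.1 supplies a length, and the separate table shells, which are not available here, may define it.

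The defence does not remove the contradiction. A deliberate three-week window would still be misnamed, and nothing readable says that it was deliberate.

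**Conclusion.** The concern holds, at minor severity. SAP 12.1, Tables 14.3.1.8 and 14.3.1.9 and Listing 16.2.7.3 call three weeks the dose titration period, while SAP 4.1 and Protocol 7.2, 9.3.1 and Table 2 limit titration to 14 days. Followed literally, the plan reports events starting on Days 15-21 as titration-period events, although every orismilast arm is by then scheduled at its assigned level. The overrun is 7 of 21 days against the 14-day ceiling, assuming Days 1-21 and the scheduled doses in Table 2.

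Two tables and one listing are affected. SAP 12 plans no inferential safety analysis, and the overall TEAE tables and all efficacy analyses are untouched.

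**What to change.** Reconcile SAP 12.1 and the two indexes with SAP 4.1 and Protocol 7.2, 9.3.1 and Table 2 in one of two ways:

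1. **Keep the window and change the name**, for example to *first 3 weeks of treatment*, with day limits stated. This needs only SAP and shell wording. The cost is that no adverse event output is then confined to titration.
2. **Keep the name and change the window** to study Days 1-14, using the SAP 7.2 definition of study day. This needs the wording plus one date cut-off. It drops the first full-dose week of 40 mg from the early display and still mixes titration and full-dose days in the lower arms. Add a footnote that both daily doses are at the assigned level from Day 8 for 20 mg and Day 9 for 30 mg.

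With either option, state the same definition of the titration period for compliance Table 14.1.5.2. The change concerns the reporting window only, not dosing.
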